- 4. Determine for whom the intervention is effective:** This novel CBT intervention for checking (CBT-C) focuses on identifying and challenging maladaptive beliefs about memory, with the aim to increase patients' confidence in their memory for checking situations. In the preliminary treatment investigation, maladaptive beliefs about memory decreased significantly across treatment, and were predictive of decreased checking behaviours at post-treatment (Alcolado & Radomsky, 2016). However, it remains unclear for whom this intervention is most effective. Are all individuals with compulsive checking plagued by maladaptive beliefs about memory, and do patients need to endorse these beliefs in order for this treatment to be effective? These questions will also be examined in this investigation, where the larger sample size will allow for comparisons based on patients' degree of endorsement of maladaptive beliefs about memory.

Hypotheses:

Following directly from the project's objectives, the hypotheses are **(1)** that the treatment (CBT-C) will be effective, in replication of a previous pilot treatment; **(2)** this brief intervention will be more effective than the comparison condition (TAU); **(3)** the effects will be maintained at 6-month follow-

up; and that (4) although the treatment will be effective for all, it will be most effective for those patients with high pre-treatment levels of maladaptive beliefs about memory.

Design/Methodology

Participants:

Participants (N = 50): n = 25 in CBT-C, and n = 25 in TAU; allowing for the testing of an additional 5 participants [predicting an approximate 10% drop-out rate as was seen in the pilot study]) will take part. This sample size is reasonable given the number of OCD referrals our clinic typically receives in a year (approximately N = 50) in conjunction with the active recruitment we will do through the community support groups, allowing for ineligible participants and study attrition. This sample size is also adequately powered for the analyses (see Power Analyses and Statistical Plan, below). Participants will come from one of two sources, either our Anxiety Disorders Clinic or community (see Recruitment, below).

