Compensation: Participants will be offered \$10 at the end of each assessment visit (for a maximum of \$30 per participant), as a monetary compensation for participants time and efforts, as well as to offset the costs of transportation for their appointments. They will not be offered compensation for their treatment visits. Compensation will be offered in-person, or, if a participant attends online visits, will be provided by mail.

Timeline:

Time point	Phone Screen	Pre-treatment Assessment	Treatment Week 1	Treatment Week 2	Post-treatment Assessment	6-mo. follow-up & debrief
Condition						
A) CBT-C	✓	✓	✓	✓	✓	✓
B) TAU	✓	✓	×	×	✓	✓

✓ = Study visit at this time point

× = No study visit at this time point

Statistical Plan:

Intent-to-treat (ITT) analyses will be conducted in order to accurately depict the progression of all participants through this treatment. As such, if there is drop-out, the last observation point for those participants will be carried forward for all subsequent missing data points of interest. To test **hypotheses 1, 2, and 3** (1 - that the treatment be effective, 2 – as compared to the control group, and 3 – that its effects last over the follow-up period), a mixed-model ANOVA will be conducted. The between-participants independent variable will be treatment condition (CBT-C vs. TAU), and the within-participants independent variable will be time point (pre-treatment, post-treatment, and 6-month follow-up). The dependent variable will be the checking subscale of the VOCI. A similar analysis using average daily time spent checking per week from the daily diaries as a dependent variable, as an alternate measure of checking.

A linear regression will be conducted to test **hypothesis 4** (that the extent to which maladaptive beliefs about memory are endorsed affect outcome). Pre-treatment BAMI total score will be entered as the predictor variable. The criterion variable will be a change score that subtracts pre-treatment VOCI score from post-treatment VOCI score. All analyses will be conducted using SPSS statistical software.

Budget details and available resources:

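### Hypothesis 4 says CBT-C works for everyone, but no planned analysis can show whether patients with low memory-belief scores benefit over TAU

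*Combined protocol and SAP*

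**What the plan says.** The Hypotheses section makes a two-part claim: "although the treatment will be effective for all, it will be most effective for those patients" whose memory-belief scores are high before treatment. Study Objectives, item 4, puts the first part as a question, "do patients need to endorse these beliefs in order for this treatment to be effective", and says that "the larger sample size will allow for comparisons based on patients' degree of endorsement of maladaptive beliefs about memory".

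The Statistical Plan restates hypothesis 4 more narrowly, as "that the extent to which maladaptive beliefs about memory are endorsed affect outcome". The universal-benefit part is gone. The analysis is a linear regression: "Pre-treatment BAMI total score will be entered as the predictor variable", and "The criterion variable will be a change score that subtracts pre-treatment VOCI score from post-treatment VOCI score". The plan has no arm term, no arm × BAMI term, no estimate at a low BAMI value and no comparison by level of endorsement. It does not say whether both arms or only CBT-C participants enter.

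Treatment effectiveness is tested under hypotheses 1–3 by a mixed ANOVA on VOCI checking: "The between-participants independent variable will be treatment condition (CBT-C vs. TAU), and the within-participants independent variable will be time point". BAMI is not part of that model.

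**The concern.** Whether low scorers benefit is a question about a controlled effect (CBT-C minus TAU) at low BAMI. The plan estimates a controlled effect averaged over BAMI, and separately an uncontrolled association between BAMI and change. Neither is the quantity in question.

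- A significant slope says that change differs with BAMI. It is compatible with benefit, no benefit or harm in low scorers.
- A non-significant slope does not show equal benefit, because no margin or confidence bound is set.
- The fitted change at low BAMI has no TAU contrast, so it mixes treatment effect with natural change and regression to the mean.

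At stake is the question of for whom the intervention works, which the protocol lists as one of four objectives. The plan could be followed exactly and still leave that half of hypothesis 4 unanswered, whichever way the slope test falls. The average comparison of CBT-C with TAU is not affected.

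**Working it through.** **1. The plan's own figure.** The power paragraph under Participants gives N = 43 for a one-predictor regression. With f² = 0.15 (conventional medium), noncentrality √(0.15 × 43) = 2.54 and 41 df, one-sided α = 0.05 gives power 0.803, so 43 is reproduced at 80% power. It is a sample size for one slope. No sample size is given for an effect in low scorers.

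**2. Why the slope cannot answer.** Let z be standardised BAMI. Suppose expected change (post minus pre; negative is improvement) is a + bz in TAU, and CBT-C adds −(m + dz). Then:

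- benefit over TAU at z = −1 is m − d;
- the slope with arms pooled 1:1 is b − d/2;
- the slope in CBT-C alone is b − d.

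The slope does not contain m. A pooled slope of −0.25 with b = 0 means d = 0.5. Benefit in low scorers is then 0.3 if m = 0.8, zero if m = 0.5, and −0.2 (harm) if m = 0.3. Adding m from the ANOVA does not settle it, because b is unknown: b = −0.25 with d = 0 gives the same pooled slope and full benefit m in low scorers.

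**3. How often the slope would miss zero benefit at z = −1.** Taken from the documents: 25 per arm, and pilot partial eta squared > .32, which gives f = √(0.32/0.68) = 0.686 and d = 2f = 1.37 if read as a two-group effect. Assumed, because not given: two-sided α = 0.05; pre–post correlation r of 0.5 to 0.7; SD of change √(2(1 − r)) = 1.00 to 0.77 baseline SD; benefit linear in BAMI with d = m, so that it is zero at z = −1. Results are by simulation; repeat runs agree to within about two percentage points.

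| Arms analysed | Average benefit m | BAMI–baseline VOCI correlation | Slope non-significant |
|---|---|---|---|
| Pooled, 50 | 0.5 SD | 0 | about 50–64% |
| Pooled, 50 | 0.5 SD | 0.3 | about 23–26% |
| Pooled, 50 | 0.8 SD | 0 | 21–35% |
| Pooled, 50 | 1.37 SD (pilot size) | 0 | about 6–11% |
| CBT-C only, 25 | 0.5 SD | 0 | 17–37% |
| CBT-C only, 25 | 0.8 SD | 0 | about 1–7% |
| CBT-C only, 25 | 1.37 SD | 0 | under 1% |

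The correlation matters because regression to the mean makes b = −0.3 × (1 − r), that is −0.15 to −0.09. This steepens the slope in both arms for reasons unrelated to CBT-C. The slope is then significant more often, but it is no more informative about low scorers.

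The shape of the benefit matters too. With SD of change 1 and zero correlation, if the whole lower half of scorers gains nothing, the slope is missed in 76% (pooled) and 56% (CBT-C only) at average 0.5 SD, 54% and 21% at 0.8 SD, and 24% and 1% at 1.37 SD. If only the lower third gains nothing, the figures are 86% and 76%, 75% and 50%, and 52% and 14%.

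**4. What a direct estimate would give.** In a model with arm, BAMI and arm × BAMI, the variance of the arm difference at z = −1 is about σ²(2/25 + 2/25) = 0.16σ², so SE = 0.4σ. With t(46) = 2.013 the 95% half-width is 0.805σ, or 0.62 to 0.81 baseline SD for σ = 0.77 to 1.00. Simulation, which allows for chance differences in BAMI between arms, gives about 0.65 to 0.83 SD. Power to exclude zero for a true low-BAMI benefit of 0.5 SD is about 23–35%.

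**The case against.** **The wording is loose.** The universal-benefit phrase is a subordinate clause, it may mean only the overall effect of hypotheses 1 and 2, and the Statistical Plan drops it. That is a fair reading of the clause alone. It does not dispose of objective 4, which asks the same question outright, says it will be examined and promises comparisons by endorsement.

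**The ANOVA covers it.** It tests an average, and a positive average can coexist with no effect in a subgroup.

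**The trial is too small.** This stands as a limit on the answer: with 23–35% power at 0.5 SD, a clear result in low scorers is unlikely. It is also a reason to fix the interpretation in advance.

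**Stronger readings that the documents do not support.**

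- A reader might infer that the plan will treat a non-significant slope as proof of equal benefit. Hypothesis 4 itself predicts a slope, and nothing in the text says how a null slope will be read.
- A reader might infer that the slope would usually miss an absence of benefit in low scorers. That depends on effect size, shape, the arms analysed and the BAMI–baseline correlation. The Background says memory beliefs relate to greater checking severity, so a zero correlation is doubtful.
- A reader might infer that low scorers would be offered or refused CBT-C on the strength of the slope. The section on potential benefits envisages offering it to waiting patients with compulsive checking generally, and the section on potential harm withholds it if it is not shown effective. Neither mentions BAMI.

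**Conclusion.** The concern holds in this form: the plan states that CBT-C works for everyone and asks whether low endorsers benefit, but specifies no analysis that can show it. This follows from the text and from the algebra in step 2, and needs no assumption about effect size.

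The size of the practical risk is uncertain. Under linear benefit that reaches zero at 1 SD below mean BAMI, the planned slope would be non-significant in about 50–64% of trials at an average benefit of 0.5 SD (arms pooled, BAMI unrelated to baseline VOCI), in about 23–26% if that correlation is 0.3, and in about 10% or less for a pilot-size effect or for CBT-C alone at 0.8 SD or more. The low figures belong to the linear shape; step-shaped benefit gives higher ones. None of these inputs is in the documents, apart from the arm sizes and the pilot effect against a waitlist. The point merits a change because the remedy is cheap; it does not threaten the main comparison.

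**What to change.** For hypothesis 4, fit change in VOCI checking on arm, pre-treatment BAMI and arm × BAMI, using both arms, and name the checking subscale as the outcome. Report the CBT-C minus TAU difference with its 95% CI at stated low and high BAMI values, for example 1 SD below and above the mean. The product term is essential: arm plus BAMI alone forces the same arm difference at every BAMI value and would merely return the average effect.

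State in advance that benefit for all will be claimed only if the low-BAMI interval excludes zero in favour of CBT-C, and that a non-significant slope or interaction will not be read as equal benefit. Otherwise delete the universal-benefit clause from hypothesis 4.

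The cost is one model on data the trial already intends to collect, and a few sentences in the Statistical Plan. The downside is precision: with a half-width of about 0.65–0.83 SD at N = 50, the answer for low scorers may have to be 'not established'.

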Inclusion criteria are that participants must be age 18 or older, with a diagnosis of OCD and clinically significant levels of compulsive checking. This is defined as being able to meet the diagnostic criteria for OCD according to the Diagnostic and Statistical Manual of Mental Disorders, 5th Edition (DSM-5; American Psychiatric Association, 2013) based solely on checking symptoms. Other OCD symptoms may be present and checking does not need to be the primary symptom. This study will be offered through online video conferencing platforms or in-person appointments to adhere to pandemic restrictions and maximum safety. If pandemic restrictions are in place, participants must be available for appointments using an online video conference platform such as Zoom, Microsoft Teams, or Doxy.

Exclusion criteria include active suicidality, psychosis, mania, or a substance use disorder that would interfere with participation in the treatment. Participants do not have to be treatment or CBT naïve, and can be medicated, as we are interested in a real-world sample. This information will be collected and tracked in case any differences become relevant for analyses.

Power analyses conducted using G*power (Faul, Erdfelder, Lang, & Buchner, 2007) indicate the sample size of 50 participants will provide more than adequate power to conduct all analyses (see Statistical Plan, below). For the ANOVAs, assuming a medium effect size, 2 conditions, 3 time points, and requiring a high level of power, an N of 44 is needed. For a linear regression with one predictor, with similar effect size and power, N = 43 is needed.

Materials:

Measures: These will include a **background information** form (including age, sex, level of education, marital status, and work status). **The MINI International Neuropsychiatric Interview** (Sheehan et al., 1998) Version 6.0 will be administered to diagnose presence of OCD and any other co-morbid conditions according to the. OCD severity will be assessed using the gold standard **Yale-Brown Obsessive Compulsive Scale** (Y-BOCS; Goodman et al., 1989a). **Validated self-report questionnaires assessing OCD symptoms** (the Vancouver Obsessional Compulsive Inventory [VOCI]; Thordarson et al., 2005), **beliefs** (Obsessive Beliefs Questionnaire [OBQ]; OCCWG, 2005), and associated **affective symptoms** (Depression Anxiety Stress Scale, DASS; Lovibond & Lovibond, 1995) will be administered. To assess beliefs about memory, the new **Beliefs about**

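### The power statement for hypothesis 4 sets N = 43 against all 50 participants, but only the 25 allocated to CBT-C inform response to CBT-C

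*Combined protocol and SAP*

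**What the plan says.** The power paragraph under Participants (Design/Methodology) claims that "the sample size of 50 participants will provide more than adequate power to conduct all analyses". Two calculations support this. One covers the repeated-measures comparison of the arms: "assuming a medium effect size, 2 conditions, 3 time points, and requiring a high level of power, an N of 44 is needed". The other covers the regression: "For a linear regression with one predictor, with similar effect size and power, N = 43 is needed". Neither the effect size nor the power is given as a number, and alpha and sidedness are not stated.

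The opening of the Participants section divides the sample as "n = 25 in CBT-C, and n = 25 in TAU", with room for 5 more to cover drop-out.

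Hypothesis 4 predicts that CBT-C will work for everyone but best for patients who start with strong maladaptive beliefs about memory. Study Objectives, item 4, presents this as a question "where the larger sample size will allow for comparisons based on patients' degree of endorsement of maladaptive beliefs about memory".

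The Statistical Plan tests it with a linear regression: "Pre-treatment BAMI total score will be entered as the predictor variable". The outcome is the pre-to-post change in VOCI. The plan does not say which participants enter the regression, and it includes neither an arm term nor a BAMI-by-arm term. The Timeline table shows no treatment visits for TAU between the pre- and post-treatment assessments.

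**The concern.** The required 43 is compared with the trial total of 50, while the hypothesis concerns an effect that only 25 participants can show. A TAU participant's VOCI change can show how BAMI relates to change without CBT-C. It cannot show how response to CBT-C varies with BAMI, except as the comparator in an interaction test, and that test is not planned.

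The stake is how a null result is interpreted. Objective 4 asks whether patients need to hold these beliefs for the treatment to work. If the protocol says power is ample, a non-significant slope could be taken as evidence that they do not, when the trial had a substantial chance of missing a medium association.

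**Working it through.** **Inputs from the documents.** Required N = 43 with one predictor; 50 participants, 25 per arm; a medium effect size; pre-treatment BAMI as predictor; pre-to-post VOCI change as outcome.

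**Assumptions (not in the documents).** Medium means f2 = 0.15 (R2 = 0.15/1.15 = 0.130, r = 0.36); alpha = 0.05. One-sided (in the predicted direction) and two-sided results are both shown.

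**Formula.** For one coefficient in a model with k terms, the test statistic follows a noncentral t with noncentrality sqrt(f2 × N) and N − k − 1 degrees of freedom.

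**1. The plan's own figure (k = 1, f2 = 0.15).**
- N = 43: noncentrality sqrt(0.15 × 43) = 2.54, df 41. Power is 80.3% one-sided and 69.8% two-sided.
- The smallest N for 80% power is 43 one-sided and 55 two-sided, so the stated figure matches a one-sided test at 80%.
- N = 50: 85.4% one-sided, 76.5% two-sided.

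The match is inferred. Other settings come close, for example r = 0.4, two-sided, 80% power (N = 44).

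**2. CBT-C arm only (n = 25, k = 1).** Noncentrality sqrt(0.15 × 25) = 1.94, df 23. Power is **59.3% one-sided, 45.8% two-sided**.

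**3. BAMI-by-arm interaction (N = 50, k = 3).** Take the treated-arm slope as above, no slope in TAU and equal residual variance. With 25 per arm, the f2 for the interaction is 0.15/4 = 0.0375. Noncentrality sqrt(0.0375 × 50) = 1.37, df 46. Power is **38% one-sided, 27% two-sided**. A simulation of 20,000 trials gave 37% and 25%.

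**4. Pooled slope in all 50, no arm term (k = 1).** If TAU has no slope, the pooled slope is half the treated slope. With an arm difference of d SD in mean change, f2 = 0.0375/(1 + 0.0375 + d²/4).
- d = 0: f2 = 0.0361; power 37% one-sided, 26% two-sided.
- d = 1: f2 = 0.0291; power 32% one-sided, 22% two-sided.

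If TAU has half the treated slope and d = 0, the mean slope is 0.75 of the treated slope. Then f2 = (0.5625 × 0.15)/(1 + 0.0625 × 0.15) = 0.0836, and power rises to 64% one-sided, 52% two-sided.

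**5. Association detectable with 80% power (r among treated patients).**

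| Analysis | Two-sided | One-sided |
|---|---|---|
| CBT-C arm, n = 25 | about 0.51 | about 0.46 |
| BAMI-by-arm interaction, N = 50, no TAU slope | about 0.63 | about 0.58 |

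The assumed medium effect is r = 0.36.

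**6. Sensitivity to the unstated effect size.** Choose f2 instead so that N = 43 gives exactly the target power:

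| Target at N = 43 | n = 25, one-sided | n = 25, two-sided |
|---|---|---|
| 80% | 59% | 55% |
| 90% | 71% | 68% |
| 95% | 80% | 77% |

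In every row, the treated arm falls at least 15 points short of the target.

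**The case against.** The best defence is that the regression, read literally with the intention-to-treat sentence, uses all 50. For a one-predictor model in 50 people, setting 43 against 50 is numerically correct. That stands: N = 43 is not a miscalculation. But the power then belongs to an association between BAMI and change in a mixed group, half of whom have had no CBT-C, which is not what hypothesis 4 asserts. The missing analysis set and arm term are a related defect, and repairing them would require a new power statement anyway.

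Four stronger readings are tempting, and the documents do not support them.

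- **Power is simply 46%.** That is the two-sided figure at an assumed f2 = 0.15. The hypothesis is directional and N = 43 matches a one-sided test at that effect size, which gives 59%. Quoting 46% alone would mix a change of sidedness with the question of whom to count.
- **Drop-out cuts the arm to 22 or 23.** The Statistical Plan carries the last observation forward, which keeps drop-outs in the analysis, and Participants allows 5 extra people. With 28 in the arm, power would be 64% one-sided or 51% two-sided.
- **TAU participants never receive CBT-C.** The Debrief section lets community TAU participants have it after taking part. What matters is that none is scheduled to receive it before the post-treatment VOCI.
- **The pooled slope must have very low power.** The 22–37% range requires no slope in TAU. TAU may include medication, psychoeducation or other therapy, so some slope is plausible and would raise the pooled figure. A TAU slope would not make the pooled coefficient specific to CBT-C.

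Nor do the documents say how a null result would be interpreted. The risk described above is a possibility, not a stated intention.

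**Conclusion.** The concern holds in a conditional form. Since 43 exceeds 25, the adequacy claim for hypothesis 4 depends on treating TAU participants as informative about response to CBT-C; that step needs no assumption about effect size. The size of the shortfall does. With f2 = 0.15 and alpha 0.05, and taking the one-sided setting that reproduces N = 43, power falls from 85% in 50 to 59% in the CBT-C arm (26 points) and to 38% for the interaction (47 points, assuming no TAU slope). The two-sided figures are 77%, 46% and 27%. A larger assumed effect narrows the gap: at the most favourable setting tried, the treated arm reaches about 80%, but against a 95% target. The documents do not fix which of these settings was intended.

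**What to change.** **Participants, power paragraph.** Limit the general adequacy claim to the analyses it fits. Replace the N = 43 sentence with the power of the hypothesis 4 analysis that will be run, either the CBT-C arm alone or a BAMI-by-arm interaction in all 50. State f2, alpha and sidedness as assumptions. Give the association detectable with 80% power: r of about 0.51 (arm) or 0.63 (interaction) two-sided, or about 0.46 and 0.58 one-sided. For the interaction, state the assumed TAU slope as well.

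**Study Objectives item 4 and Statistical Plan.** Name the same analysis and its participants. Report the BAMI slope (or the difference in slopes) with its 95% confidence interval. State that a non-significant result will not be read as showing that memory beliefs do not matter for response. Labelling hypothesis 4 exploratory is optional.

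**Cost.** A few sentences and a less favourable stated power for one hypothesis. No extra participants, visits or staff, and no change to enrolment.

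### At a conventional medium effect, the regression's N = 43 matches only a one-sided 80% calculation; two-sided, 80% power needs N = 55 and the planned 50 gives about 76%

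*Combined protocol and SAP*

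**What the plan says.** The power paragraph under Participants (Design/Methodology) gives two sample sizes from G*Power.

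- The ANOVA calculation takes a medium effect with two groups and three assessments; its result is given as "requiring a high level of power, an N of 44 is needed".
- The regression result is given as follows: "For a linear regression with one predictor, with similar effect size and power, N = 43 is needed".

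From these it concludes that "the sample size of 50 participants will provide more than adequate power to conduct all analyses".

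The Statistical Plan identifies the regression as the test of hypothesis 4: "Pre-treatment BAMI total score will be entered as the predictor variable", and the outcome is the pre-to-post change in VOCI score. It says nothing on whether the test is one- or two-sided. Neither section gives a number for the effect size, the power, alpha or the correlation between repeated measures.

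**The concern.** The two sample sizes are almost equal and are presented as resting on matching assumptions. A between-within ANOVA with three repeated measures and a simple regression gain precision in different ways, so near-equal sample sizes at the same nominal effect and power would be a coincidence worth checking.

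What is at stake is the stated power for one of the four hypotheses, the one about which patients benefit most. If 43 is a one-sided 80% figure and the analysis is run two-sided, as regression output usually is, the trial falls short of 80% power for that hypothesis while its protocol calls the power more than adequate.

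**Working it through.** **Inputs**

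- Stated sample sizes: 44 (ANOVAs) and 43 (regression), from the power paragraph.
- One predictor; two conditions and three time points, from the power paragraph and the Statistical Plan.
- Planned N = 50, from Participants. The Statistical Plan carries last observations forward, so dropouts stay in the analysis.
- Assumed, because the plan gives no numbers: Cohen's medium effects (f² = 0.15 for regression, f = 0.25 for ANOVA) and alpha 0.05. One- and two-sided tests and powers of 80 to 95% were tried.

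**Step 1. Reproduce the regression figure.** For one predictor the test has N − 2 degrees of freedom. The noncentrality is λ = f²·N for the two-sided F test and √λ for the one-sided t test. At N = 43, √(0.15 × 43) = √6.45 = 2.54. Against the one-sided 5% critical value of 1.683 (41 df) the power is 80.3%; N = 42 gives 79.5%. So 43 is exactly the smallest N for a one-sided 5% test with 80% power.

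**Step 2. Try the other readings at f² = 0.15.** Smallest N:

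| Power | One-sided 5% | Two-sided 5% |
|---|---|---|
| 80% | 43 | 55 |
| 85% | 50 | 62 |
| 90% | 59 | 73 |
| 95% | 74 | 89 |

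No other cell gives 43. (A two-sided test at 10% also gives 43 for 80% power; it has the same critical value as the one-sided 5% test.)

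**Step 3. Power at the plan's sample sizes, f² = 0.15.**

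| N | λ = 0.15·N | Two-sided power | One-sided power |
|---|---|---|---|
| 43 | 6.45 | 69.8% | 80.3% |
| 50 | 7.50 | 76.5% | 85.4% |
| 55 | 8.25 | 80.5% | 88.3% |

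**Step 4. Vary the effect size.** Reading medium as r = 0.3 (f² = 0.099) needs N = 82 for two-sided 80% power. Carrying f = 0.25 over literally (f² = 0.0625) needs 128. In the other direction, a two-sided test at N = 43 has 95% power only if f² = 0.317 (r = 0.49), about twice the medium value. A two-sided test at N = 50 reaches 80% power if f² is about 0.164 rather than 0.15.

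**Step 5. Compare with the ANOVA figure.** For the condition-by-time interaction, λ = f²·N·m/(1 − ρ), with m = 3 measures, correlation ρ, sphericity, and degrees of freedom 2 and 2(N − 2). With ρ = 0.5 and N = 44, λ = 0.0625 × 44 × 3/0.5 = 16.5 and the power is 95.6%. N = 42 gives 94.6%, so 44 is the smallest equal-arm total for 95%. At the same ρ, 80% would need 28 and 90% would need 36. But ρ is not stated, and 44 is also the smallest equal-arm total for other pairs:

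| Assumed ρ | Nominal power that gives N = 44 |
|---|---|
| 0.2 | 80% |
| 0.3 | 85% |
| 0.4 | 90% |
| 0.5 | 95% |

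**The case against.** The strongest reply is that the plan's two figures can be made to agree. With a correlation of about 0.2 the ANOVA needs 44 for 80% power, and a one-sided regression needs 43 for 80%. Hypothesis 4 is directional, so a one-sided test is defensible, and at N = 50 it has 85.4% power. This stands as a possibility, so the statement about similar power cannot be called false on every reading. It does require two choices that the plan does not declare, and 80% fits awkwardly with "requiring a high level of power".

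It is also fair that the two-sided shortfall is modest (76.5% against 80%), that it concerns the fourth hypothesis and not the main comparison of conditions, and that no estimate changes.

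Several stronger readings are tempting, but the documents do not support them:

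- *The ANOVA was sized at 95%, so the regression needed 89.* The 95% is a back-calculation from an assumed correlation of 0.5; the plan states neither number.
- *Power is lower still because of dropout.* The plan carries last observations forward, so the analysis keeps all 50.
- *Power should be judged on the 25 CBT-C patients.* The Statistical Plan does not restrict the regression to that arm. Whether it should is a separate question about the analysis population and does not bear on the arithmetic of 43.
- *A null result will be read as showing that memory beliefs do not matter.* The documents contain no such interpretation rule.

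**Conclusion.** The point holds in this form. Given f² = 0.15 and alpha 0.05, N = 43 is a one-sided 80% figure, and the plan declares no one-sided test. For an ordinary two-sided test, every power level from 80% upward needs at least 55 patients, more than the planned 50, so the claim of more than adequate power for all analyses is unsupported for hypothesis 4. This conclusion does not depend on what power the ANOVA used. It does depend on the conventional medium effect: a smaller reading makes the gap wider, and an f² of about 0.164 or more closes it at 80%.

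The mismatch with the ANOVA is a weaker statement. It follows under the common assumption of correlation 0.5 and sphericity, and it remains an inference until the plan gives its inputs.

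**What to change.** Replace the regression sentence with one of the following.

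- *For a one-predictor regression with a medium effect (f² = 0.15) and two-sided alpha 0.05, N = 55 is needed for 80% power; N = 50 gives about 76%.*
- Or declare in advance, with a reason, that the hypothesis 4 test is one-sided at 5%, and state that N = 50 gives 85% power at f² = 0.15.

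For both calculations, state alpha, sidedness where it applies, the numeric effect size and the power; for the ANOVA, also state the assumed correlation and sphericity. Remove the claim of more than adequate power for all analyses. Report the hypothesis 4 coefficient with its confidence interval, so that a non-significant result shows which effects remain compatible with the data. Labelling the hypothesis exploratory is an option but not required.

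The cost is a few sentences and a less favourable stated power. Enrolment and the analysis model do not change.
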